#### 11.4.3 Secondary Analyses

- Switching to superiority test will be considered as recommended by the CPMP (2001):

*"If the 95% confidence interval for the treatment effect not only lies entirely above  $-M$  but also above zero then there is evidence of superiority in terms of statistical significance at the 5% level ( $P < 0.05$ ). In this case it is acceptable to calculate the  $P$  value associated with a test of superiority and to evaluate whether this is sufficiently small to reject convincingly the hypothesis of no difference."*

- Hearing loss degree will be added in post hoc analysis as a covariate.

#### 11.4.4 Interim analyses

No interim analysis is planned according the test design.

#### 11.4.5 Safety analysis

Safety analysis is foreseen to be accomplished with the interview by the PI during the trial. Clinical judgement from the PI will be used for the safety evaluation.

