Objective(s):	The purpose of this research is to show that the performance of the device is as good as or better than the current device or previous hearing aid generation. Furthermore, speech should not be negatively affected with the addition of the new feature, the usability of the devices (that end users are able to handle the devices) should be as good as the current device, and there should be no artefacts or unwanted noises. Some measurements serve as quality control prior to product launch.

Outcome(s):	
Primary Endpoint:
 

Primary Outcome is the speech intelligibility with the investigational device compared to the current device (using speech tests)

 
Secondary Endpoints:
 

Comparing the subjective performance of the investigational device to the current device (using questionnaires)

Speech intelligibility with the new feature on and off (using speech tests)

Handling/usability of the devices (specified questionnaire)

Subjective preference testing (using interviews)

Procedural safety meaning that there are no unwanted noises or artefacts heard from the devices (as reported by the subjects)

 
Scores from speech tests and questionnaires should be as good as or higher than with previous devices. Handling of the devices should be the same or easier than previous devices. No unexpected, unwanted behaviour from the devices should occur.

Study design:	This is a controlled, open label, comparative clinical investigation conducted monocentric at the premises of Bernafon in Bern, Switzerland.

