### 4.2 Primary Objective

The study seeks primarily to determine if the performance of the IMD is as good as the RMD. As a second primary objective the study seeks to proactively determine if there is any unknown and/or unwanted behavior from the IMD. The study seeks to validate that the performance of the IMD is as expected in comparison with the RMD, meaning that the performance of the IMD should not be inferior to the RMD.

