The following appointments will include a series of field tests with corresponding lab test appointments. There could be up to 6 appointments, but will not exceed 2 hours each time. During these appointments they will participate in speech testing, listening effort testing, perceived loudness testing, and subjective evaluations of sound and benefit of the hearing aids. Subjects will be given questionnaires and diaries to complete with all field test periods.

After they have completed all appointments the clients will receive instructions about the continued use of the RMD and the reminder that they are welcome to come to the clinic for any maintenance of the aids.

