## 8. STUDY INTERVENTION

### 8.1 Identity of Investigational Products (medical device)

The treatment will be approximately 4 months of use with the IMD and breaks in between when they will return to the RMD. All participants will already be Bernafon hearing aid users; therefore, during the investigation they will stop using RMD and switch to the IMD for the assigned periods.

Additionally, there will be lab tests in which the participants will use the IMD for up to 2 hours at a time during testing in the clinic.

There are 3 field tests planned. In between each field test they will return to wearing RMD. At the end of the entire trial, and once the devices have been CE marked, the participants will have the choice to continue wearing the RMD or to switch and wear the IMD permanently.

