### 9.3.2 Second Visit

Visit 2, Testing, Day 14 +/-3: The subjects will hand in the completed questionnaire given to them at the previous appointment. The clinician will conduct an interview based on the comments in the diary and prepared questions about user experience. They will be asked which pair of hearing aids they preferred. A lab test will be made to test speech intelligibility with the OLSA and WAKO tests (all features besides [REDACTED] will be set to off for the Lab testing). They will return the IMD and be instructed to use the RMD until the next appointment. Any AEs will be reported in the CRFs. They will be scheduled for the next visit.

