3.3 Switching to superiority hypothesis

If the confidence interval for the difference between both devices lies entirely above 0, then "it is acceptable to calculate the P value associated with a test of superiority and to evaluate whether this is sufficiently small to reject convincingly the hypothesis of no difference. There is no multiplicity argument that affects this interpretation because, in statistical terms, it corresponds to a simple closed test procedure. Usually this demonstration of a benefit is sufficient on its own, provided the safety profiles of the new agent and the comparator are similar."

Reference: Committee for Proprietary Medicinal Products (CPMP). (2001). Points to consider on switching between superiority and non-inferiority. British Journal of Clinical Pharmacology, 52(3), 223–228.

4. Required sample size

Reference: Chow S, Shao J, Wang H. 2008. Sample Size Calculations in Clinical Research. 2nd Ed. Chapman & Hall/CRC Biostatistics Series. page 52.

With the following requirements: non-inferiority margin: 1.34, standard deviation: 2 dB, alpha: 0.025, beta: 0.1.

Required sample size:

```
delta <- n.i.m.

sd <- reviewSummary$standev[reviewSummary$study=="16REF"]

alpha <- 0.025

beta <- 0.1
```

out.sample.size <- (sd*(qnorm(1-alpha)+qnorm(1-beta))/delta)^2 ceiling(out.sample.size)

[1] 24

A sample size of 24 will be use to test the non-inferiority hypothesis with a non-inferiority margin of 1.3 dB.

5.References

Alworth, L. N., Plyler, P. N., Reber, M. B., & Johnstone, P. M. (2010). The effects of receiver placement on probe microphone, performance, and subjective measures with open canal hearing instruments. Journal of the American Academy of Audiology, 21(2010), 249–266. http://doi.org/10.3766/jaaa.21.4.4

Committee for Proprietary Medicinal Products (CPMP) (2001). Points to consider on switching between superiority and non-inferiority. British Journal of Clinical Pharmacology, 52(3), 223–228.

D'Agostino, R. B., Massaro, J. M., & Sullivan, L. M. (2003). Non-inferiority trials: design concepts and issues - the encounters of academic consultants in statistics. Statistics in Medicine, 22(2), 169–86. http://doi.org/10.1002/sim.1425

Del Re, A. C. (2015). A Practical Tutorial on Conducting Meta-Analysis in R. The Quantitative Methods for Psychology, 11 (1), 37-50.

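### Unwanted device behaviour is a primary objective with no planned estimate, and the data rules as written could drop the participants most affected

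*Protocol*

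**What the plan says.** **Status of the objective.** Protocol 4.2: "As a second primary objective the study seeks to proactively determine if there is any unknown and/or unwanted behavior from the IMD". The synopsis adds a success statement, "No unexpected, unwanted behaviour from the devices should occur", but lists subject-reported noises and artefacts among the secondary endpoints. Section 5.1 gives the speech reception threshold (SRT) as the only primary outcome, and 5.4 treats unexpected device events as a safety outcome.

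**Recording.** Section 5.4 names the events of interest (feedback, artefacts, discomfort, muting, unexplained signals, loud sounds, occlusion) and uses a diary. Section 6.1: "Subjects will be given questionnaires and diaries to complete with all field test periods". Under 9.3.1, 9.3.3 and 9.3.5 the diary goes out at Visits 1, 3 and 5, each of which starts a period of IMD wear. Sections 10.1 and 10.1.1 add adverse events (AEs) collected by the clinician at each visit, covering both the IMD and the reference device (RMD), with graded severity and causality. Under 10.1.2 serious events and device deficiencies go to the sponsor within 24 hours for its own assessment.

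**Analysis.** Section 11.4.5 consists of the investigator's interview and this sentence: "Clinical judgement from the PI will be used for the safety evaluation". The SAP deals only with SRT non-inferiority and a possible switch to superiority.

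**Whose data count.** Section 8.5 bars withdrawn participants' data from any final analysis or report. Section 10.1 withdraws participants whose pain prevents use, in part so that partial data are removed. Section 11.5 restricts analysis to complete cases. Sections 7.4 and 8.3 say that data from participants who withdraw or discontinue are used.

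**Exposure.** Section 8.1: "The treatment will be approximately 4 months of use with the IMD and breaks in between when they will return to the RMD". The study schedule shows three field periods of 14 days, the last ending on Day 59.

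**The concern.** An objective ranked as primary should have a stated summary: who is counted, what counts as an event, and how uncertain the answer is. Here there is none. Diary entries, visit AEs and deficiency reports will be collected, but the report could end in a sentence of clinical opinion with no number behind it. Whether the synopsis expectation of no unwanted behaviour was met would then depend on the reader's trust in that opinion.

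The data rules make this worse. A participant who gives up the IMD because of whistling, occlusion or pain carries the most relevant information for this objective. Under 8.5, 10.1 and 11.5 that participant leaves the analysis; under 7.4 and 8.3 the same participant stays. If the first group of sections governs, exclusion depends on the outcome itself, and the error runs in one direction, towards finding nothing.

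**Working it through.** **1. The plan's own figure.** Neither document sizes the study for unwanted behaviour. The only sizing is for SRT (Protocol 11.2, SAP 4): n = (sd × (z₀.₉₇₅ + z₀.₉₀) / δ)². With sd = 2 and δ = 2 − 1.31/2 = 1.345, n = (2 × 3.2415 / 1.345)² = 23.2, so 24. The SAP's stated 1.34 gives 23.4, also 24; the rounded 1.3 gives 24.9, so 25. The stated 24 is reproduced from the unrounded margin. Below, 24 serves as the lower number of participants and the synopsis's approximate enrolment of 35 as the upper.

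**2. What zero events can show.** With 0 of n affected, the exact upper limit is 1 − 0.025^(1/n) (two-sided 95%) or 1 − 0.05^(1/n) (one-sided 95%).

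| n | two-sided | one-sided |
|---|---|---|
| 35 | 10.0% | 8.2% |
| 24 | 14.2% | 11.7% |

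**3. Chance of seeing at least one affected participant**, 1 − (1 − p)ⁿ. The true proportions p are assumptions, since the documents give none.

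| p | n = 35 | n = 24 |
|---|---|---|
| 1% | 30% | 21% |
| 2% | 51% | 38% |
| 5% | 83% | 71% |
| 10% | 97% | 92% |

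**4. The data rules side by side.**

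| Section | Treatment of the data |
|---|---|
| 8.5 | withdrawn: kept in the database, not analysed or reported |
| 10.1 | pain preventing use: withdrawn, partial data removed |
| 8.4 | too little IMD wear: data not used |
| 11.5 | complete cases only |
| 7.4 | withdrawn: data used |
| 8.3 | discontinued at own request: data included |

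None of these sections separates safety data from SRT or questionnaire data, so the conflict extends to safety.

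**5. What the exclusion could do.** Assume that k of 35 stop because of a device problem and that no one else reports an event. Intervals are exact two-sided 95%. The last column is 1 − 0.025^(1/(35 − k)).

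| k | all fitted counted | stoppers excluded | upper limit |
|---|---|---|---|
| 1 | 1/35 = 2.9% (0.1% to 14.9%) | 0/34 | 10.3% |
| 3 | 3/35 = 8.6% (1.8% to 23.1%) | 0/32 | 10.9% |
| 5 | 5/35 = 14.3% (4.8% to 30.3%) | 0/30 | 11.6% |

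In each row the observed proportion falls to zero. At k = 5 the upper limit from the reduced set lies below the proportion among all fitted.

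**6. Exposure.** IMD: 14 + (38 − 24) + (59 − 45) = 42 days, or 35 × 42 = 1,470 person-days. RMD intervals: (24 − 14) + (45 − 38) = 17 days. Together 42 + 17 = 59 days. At 30 days a month, 4 months is 120 days, so 8.1 does not match the schedule even with the breaks included.

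**The case against.** The strongest reply is that safety is monitored more fully than 11.4.5 suggests. AEs are collected at every visit, including Visits 3 and 5, which close the RMD intervals. Severity and causality have defined scales, and the sponsor independently assesses serious events and device deficiencies. The study calls itself exploratory, the devices are presented as low risk, and the question in 4.2 concerns the IMD alone. Section 5.4 sees the diary as a way to alert the sponsor, and 9.2.4 offers a qualitative benchmark: none of these events in testing of previous products.

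Most of this stands, and it rules out several stronger readings that a reader might draw:

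- *That the diary is the only record, or that nothing is captured on the RMD.* Sections 10.1 and 10.1.1 say otherwise. The RMD record is less sensitive, with no diary and no scheduled interview at Visits 3 and 5, but it exists.
- *That the investigator's opinion is the only judgement.* Section 10.1.2 gives the sponsor its own assessment.
- *That the objective cannot be answered without an RMD rate.* Finding unwanted IMD behaviour does not logically need one. An IMD–RMD diary difference would also be hard to interpret: the RMD intervals always follow IMD wear, participants have at least 6 months' familiarity with the RMD, and they know which device they wear.
- *That SAP 3.3 makes superiority depend on a safety comparison.* The words "provided the safety profiles of the new agent and the comparator are similar" are part of quoted guidance. Protocol 11.4.3 does not repeat them, and section 11 does not expect superiority.
- *That zero reports would be claimed as proof of absence.* No section says so.

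The reply does not supply an analysis. Good collection with no stated numerator, denominator or analysis set still leaves the objective without an estimate, and the conflict over withdrawn participants is untouched.

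**Conclusion.** The point holds and should be acted on. A second primary objective is evaluated by interview and judgement alone, its rank differs between 4.2, the synopsis and 5.1, and the records already planned feed no proportion, denominator or interval. If 8.5, 10.1 and 11.5 govern, the safety result is biased towards no events; if 7.4 and 8.3 govern, it is not. The documents do not settle which.

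As to size, a clean result would leave a true proportion of up to 10.0% (35 participants) or 14.2% (24) open. In the assumed example, excluding three stoppers turns 8.6% into an observed zero. The limits treat participants as independent, count each once per event type and take reporting as complete. The numbers stopping and the true proportions are assumptions. The exposure mismatch in 8.1 is a smaller matter, relevant because any rate needs a defined wear-time denominator.

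**What to change.** - **11.4.5, safety set:** everyone ever fitted with the IMD, including those who withdraw, stop early or wear it little. Reconcile 8.5, 10.1 and 11.5 with 7.4 and 8.3 for safety data, and say whether the low-wear rule in 8.4 applies to it.
- **11.4.5, table:** for each event type in 5.4, participants with at least one event out of the safety set, with an exact 95% interval, and events per IMD wear-day from the software log described in 8.4. Draw on diary, AE and device-deficiency records together. Keep the investigator's judgement for causality.
- **RMD intervals:** list events reported at Visits 3 and 5 descriptively. An RMD diary is optional, and any IMD–RMD contrast should be labelled descriptive only.
- **Status:** align 4.2, the synopsis and 5.1 on the rank of this objective.
- **Exposure:** reconcile the length of IMD use in 8.1 with the scheduled field periods.

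The cost is one descriptive table and some text edits. The CRF content list in 12.1.1 has no wear-time field, so logged wear would need an entry when the devices come back. No extra visit or participant is needed.

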#### **11.4.6 Deviation(s) from the original statistical plan**

Any deviation from the original protocol has to be justified and reported in the final report. Post hoc analysis can be done on secondary outcomes and reported in the final report.

#### **11.5 Handling of missing data and drop-outs**

For missing data, the PI will contact the involved subject to evaluate the possibility of getting missing data from a questionnaire by post. If a test subject cannot come to the evaluation visit, after exhausting all the possibilities to reschedule a new one, the devices will be sent back per post. If a subject does not want to adhere to the protocol, he can easily switch back to his own device (RMD) and return the IMD.

Data will be immediately removed if the PI has some doubts about the data accuracy (especially about the understanding of the APHAB questionnaire).

Dropouts will not be replaced; therefore, extra subjects over the calculated sample amount will be included from the beginning to ensure enough completed cases with all data.

Analysis will be done on the complete case only.

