## 6. STUDY DESIGN

### 6.1 General study design and justification of design

This is a controlled, randomized, open label, comparative clinical investigation conducted monocentric at the premises of Bernafon in Bern, Switzerland.

The exploratory study is based on a population of hearing impaired people that have hearing loss appropriate for the IMD.

As an RMD the subjects' current hearing instruments (Bernafon device) will be used. Additionally, a control situation may be when an unaided test condition is used or a test condition with a feature on or off.

There is no placebo or "fake" device that does not provide amplification. A single group assignment design is used with test subjects that have worn the RMD for at least 6 months and will now be fit with the IMD. Most of the testing will be unblinded as the subjects are familiar with the RMD which will be used as the control. They will recognize when they are using a different device. In situations where one device is used but programmed with two different programs the test subjects will be blinded. They will not be told the difference between the two programs. They will, for example, have a feature on in one and off in another.

A randomized test order will be used to test in a simulated environment. The test subject will be tested using unaided and aided conditions in a randomized manner for speech testing, listening effort, and subjective evaluations of sound and benefit perception. Or as stated above, the testing may be single-blinded by using only the IMD and programming different states into the device for comparison testing in which the test subject will not be aware of the differences.

The participants will be expected to participate for approximately 4 months for a combinations of field tests and lab tests. For lab tests they will not spend more than 2 hours in the clinic for testing, but will be expected to come for 5-6 sessions. Field trial periods will not last more than 14 +/-3 days.

The sequence will begin with the preparation phase in which participants are invited to the clinic for testing to determine if they are candidates for the trial. The entire test procedure will be explained, and they will be given a Patient Informed consent form read which will need to be signed, dated, and returned before any testing begins.

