### **6.2.2 Blinding procedures**

The subjects will know that there are two programs (or two pairs of aids), but they will not know what the differences between them are. The program setting/device set up will be randomized so that not all test subjects have the same setting of [REDACTED] for program one and for program two. For example, program/device one may have [REDACTED] programmed for some subjects and for others program/device two will have [REDACTED] programmed. This will also help control any bias toward one program. The PI will be blinded concerning the two sets of devices. The statistician will create the randomization list and any pre-programming of devices needed to blind the PI.

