## **6.3 Unblinding Procedures (Code break)**

The statistician will maintain the documentation of blinding procedures. The [REDACTED] feature testing will be blinded and will be managed by the statistician. For all other testing the difference between the IMD and the RMD will be clear to the subjects due to the differences in hardware.

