#### 11.4.1 Datasets to be analyzed, analysis populations

Analysis population: a single group that had the same treatment (per protocol set).

The included subjects are experienced hearing aid users (minimum 6 months) with the same hearing aid model across the population. As hearing loss does not normally fluctuate, we assume that their hearing capabilities are stable over time and that the performance with a hearing aid can be compared over a longer period without any wash out period. Subjects' individual auditory capacities (hearing loss degree, noise tolerance, speech recognition) vary, however the sample is considered as a homogenous population regarding their experience with the RMD. It will be ensured that the acceptance to generic amplification via hearing aids is not tested but an actual evaluation of the difference between the RMD and the IMD. A single assignment treatment will be considered representative of clinical intervention, i.e. when an experienced hearing aid user acquires a new device.

[figure not shown]

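### Protocol 11.5 lets the PI delete data on doubt alone, in an open-label device comparison and with no analysis that restores the deleted values

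*Protocol*

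**What the plan says.** Protocol 11.5 sets the removal rule: "Data will be immediately removed if the PI has some doubts about the data accuracy". A parenthesis adds the emphasis, "especially about the understanding of the APHAB questionnaire". The same section ends with "Analysis will be done on the complete case only", and says of losses: "Dropouts will not be replaced; therefore, extra subjects over the calculated sample amount will be included from the beginning". Section 11.4.1 names a per-protocol set as the only analysis population. The SAP has no section on missing, doubtful or excluded data.

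On who knows what, section 6.1 calls the study open label. Section 6.2.2 says "The PI will be blinded concerning the two sets of devices"; those sets are the IMDs with the new feature on and off. Section 6.3 says of the rest: "For all other testing the difference between the IMD and the RMD will be clear to the subjects due to the differences in hardware". The CRF table in 12.1.1 lists the PI as author of every field, including the OLSA results that give the SRT.

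**The concern.** The rule asks only for doubt. It gives no objective test of invalidity, does not mask the decision to device or score, and plans no analysis that puts the removed value back. The primary test is a paired comparison of RMD and IMD thresholds, so one lost SRT removes that participant from the complete-case analysis.

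If the value and the device are both visible when the doubt arises, removal can depend on the result. Removal that falls mainly on results unfavourable to the IMD would shift C−T upwards and make a false non-inferiority claim more likely. Section 1.1 says the sponsor will use the results to prove the new device's performance, which makes that direction plausible. A reader of the final report could not judge the effect, because nothing requires the removed values to be shown.

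**Working it through.** **1. Does the rule reach the primary outcome?** Yes. The word introducing the APHAB gives it emphasis and does not limit the rule to it. The sentence speaks of data in general, and nothing else in 11.5 exempts the SRT.

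**2. Can the decision-maker know the device?** This is an inference. The study is open label (6.1), PI blinding is stated only for the feature comparison (6.2.2), and the PI records the OLSA results (12.1.1). Section 6.3 speaks only of what is clear to the subjects. No passage masks the PI to IMD versus RMD.

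**3. Do other provisions close the gap?**
- The audit table (12.2.2) logs changes to values already in the database. CRFs are completed after the visit (12.1.2) and data are accepted only after a plausibility check (12.2.4), so a doubted value might never be entered.
- Source data verification (12.3) is 100% for 10 patients and 50% for another 10, against about 35 planned. The list of items verified for all patients does not name the SRT.
- Deviations must be justified and reported (11.4.6), but a removal under 11.5 follows the protocol and so is not a deviation.

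These make removal of entered data partly traceable. They do not prevent it.

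**4. The plan's own sample size.** Inputs from protocol 11.2 and SAP section 4: SD 2 dB, one-sided alpha 0.025, power 90%, margin 1.3 dB (1.34 dB in the SAP).

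n = [SD × (z₀.₉₇₅ + z₀.₉₀) / δ]² = [2 × (1.960 + 1.282) / δ]²

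- δ = 1.3: 24.87, rounded up to 25.
- δ = 1.34: 23.41, rounded up to 24.

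The stated figure of about 24 is reproduced, so these inputs are used below.

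**5. Effect of removal on the error rate.** Paired differences C−T were simulated with true mean −1.3 dB (the null boundary) and SD 2 dB. After k pairs were removed, a one-sided t-test against −1.3 dB was run at 0.025. The documents do not say how many values would be doubted, so k = 1, 2 and 3 are assumptions. With no removal the rate is 2.5%.

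| Pairs removed | n | k = 1 | k = 2 | k = 3 |
|---|---|---|---|---|
| Worst IMD SRT | 35 | 2.9–3.6% | 3.4–4.7% | 3.8–6.0% |
| Worst IMD SRT | 24 | 3.0–3.7% | 3.6–4.9% | 3.8–6.2% |
| At random from the third with lowest C−T | 35 | 3.8% | 5.7% | 8.4% |
| At random from the third with lowest C−T | 24 | 4.0% | 6.3% | 10.1% |
| Lowest C−T | 35 | 6.4% | 12.3% | 20.1% |
| Lowest C−T | 24 | 7.2% | 14.5% | 24.1% |

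The first two rows need a between-subject SD, which the documents do not give; 2 to 5 dB was assumed. Each participant has a common level, plus independent variation of equal size under each device (SD √2 dB each, so that the difference has SD 2 dB). The inflation is smaller here because a poor IMD score often goes with a poor RMD score. Placing more of the variation in the IMD score raises these rows, but in the checks run they stay below the lowest-C−T rows.

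In the lowest-C−T rows the mean shifts towards the IMD by 0.13, 0.23 and 0.33 dB (n = 35), or 0.17, 0.32 and 0.45 dB (n = 24).

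**6. Removal unrelated to results.** The error rate stays at 2.5%. Starting from 35 participants, power for a true difference of zero falls from 96.2% to 95.7%, 95.2% and 94.5% for one, two and three removals.

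**The case against.** The best defence is that the sentence is about questionnaires: the only example is misunderstanding of the APHAB, a secondary outcome, and no passage describes discarding an OLSA result. That is a fair reading of intent and it lowers the severity. It does not change what the wording permits for the SRT.

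Second, removal is to be immediate, and the three conditions are run in one session in Latin-square order (11.4.2), so the contrast C−T may not exist when a value is doubted. This stands against the lowest-C−T rows as an expected outcome. It stands less well against removal of a poor IMD score, which needs no contrast.

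Third, a reader might infer that 6%, 12% and 20% (or 7%, 15% and 24%) are what one to three removals would do. They are not. Those figures require selection on the final difference and lie close to a worst case. If poor IMD scores are the ones doubted, the inflation is modest.

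Fourth, a reader might infer that the rule will favour the IMD, or that the protocol states that the PI is unblinded. The documents support neither as fact. An implausible RMD score can be doubted too, which pushes the other way, and the PI's knowledge of the device is inferred from the design.

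**Conclusion.** The point holds as a weakness of the rule. It does not show that the result will be biased. Protocol 11.5 permits removal of primary-outcome values on doubt alone, without criteria or masking, and the complete-case analysis never restores them. Existing controls make such removals partly visible at most.

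For one to three removals at the margin, false non-inferiority rises from 2.5% to about 3–6% if the worst IMD scores go. It rises to about 6–20% (n = 35) or 7–24% (n = 24) if the pairs with the lowest C−T go. These figures rest on the plan's SD of 2 dB, normal differences, an assumed number of removals and, for the lower range, an assumed between-subject SD of 2–5 dB. They illustrate what is possible and do not forecast it.

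This should be fixed. The stated emphasis on a secondary questionnaire and the modest inflation under the likelier mechanism keep it below a must-fix.

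**What to change.** Replace the removal sentence in 11.5 with:

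> A recorded value is not deleted because of doubt about its accuracy. The doubt is flagged with a written reason at the visit. The primary analysis keeps flagged RMD and IMD SRT values of participants in the per-protocol set, unless they meet technical invalidity criteria fixed in advance and applied equally to all three test conditions. A technically invalid run is repeated in the same session, the repeat is analysed and the first value is retained in the database. A sensitivity analysis excludes flagged values, and the final report lists all flags and invalid runs by device.

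Apply the same flag-and-keep rule to the APHAB.

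Two neighbouring provisions need aligning. State how the new text fits with the wear-time exclusion in 8.4. Reconcile 7.4 and 8.3, which use withdrawn participants' data, with 8.5, which does not; they determine the same analysis set.

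The cost is one paragraph, a flag field in the eCRF, a short list of invalidity criteria and one sensitivity analysis. The downside is that a few noisy values stay in the primary analysis.
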